6.5.1 MANAGEMENT OF BLEEDING EVENTS

rNAPc2 is expected to be dosed in-hospital on Days 1, 3 and 5; half-life of rNAPc2 following the day 5 dose is approximately 72 hours. Heparin is expected to be dosed in-hospital; half-life of LMWH is approximately 4½ hours, half-life of UFH is approximately 1 hour. If serious bleeding occurs in-hospital the following routine measures should be considered:

- Delay the next study drug administration or discontinue treatment if indicated.
- Consider the usual treatment measures for bleeding events, including fluid replacement and hemodynamic support, blood transfusion, and fresh frozen plasma, if physical examination and laboratory testing suggest benefit could be obtained.

If rescue management is required, participant should remain blinded to treatment assignment if possible. For uncontrolled major bleeding in a patient receiving rNAPc2 for whom usual treatment measures have been ineffective, recombinant activated clotting factor VII (rFVIIa) may be administered.²⁶ In a Phase 1 study in healthy volunteers, administration of rFVIIa 4 hours after rNAPc2 normalized PT, which was correlated with the activation of the coagulation cascade as measured using

biochemical markers of factor X and factor IX activation. This study suggests that rfVIIa may be useful in transiently reversing the anticoagulant effects of rNAPc2. However, the effect of rfVIIa in an actively bleeding patient who has received rNAPc2 is currently unknown (refer to the Investigator Brochure).

If the participant is not hospitalized, a serious bleeding event should be referred for evaluation at the appropriate facility such as an urgent care center or emergency department depending on the severity of the bleeding.

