- Central laboratory samples, if not already collected at Day of Hospital Discharge

Day of Hospital Discharge

The following procedures will occur on the Day of Hospital Discharge:

- Concomitant medication (may be obtained/extracted from the medical record to minimize staff exposure to COVID-19)
- Study medication administration, if applicable
- Local laboratory values, if applicable
- Assess need for inpatient medical services and complete ACTT
 - The need for inpatient medical services should be assessed daily after randomization until the participant is discharged from the hospital, deceased, or Day 30 visit is reached.
 - Documentation pertaining to this assessment must be provided to the CEC as outlined in the Site Manual.
- Clinical events and adverse events assessment
 - Assess for the occurrence of any adverse events and report via the eCRF as appropriate. See [Section 8.4 Adverse Events and Serious Adverse Events](#) for more information about adverse events.
 - Assess for the occurrence of any clinical event that suggests the possibility that an efficacy outcome event has occurred. See [Section 8.2 Efficacy Assessments](#) for more information about clinical events of interest.
- Post-COVID functional status (PCFS) scale
 - If hospital discharge occurs before Day 30, PCFS assessment should be performed the day after hospital discharge (up to 3 days after discharge allowed).
 - PCFS scale may be performed remotely e.g. by telephone.

- A retrospective assessment of PCFS pre-COVID-19, which reflects functional status during the month preceding COVID-19 infection, should be performed after current PCFS assessment at hospital discharge.
- Healthcare Resource Utilization Assessment
- Central laboratory samples, if Day of Hospital Discharge is prior to Day 8

Day 30 Visit (+/- 3 Days)

The following procedures will occur at the Day 30 visit:

- Visit procedures other than central lab assessment may be performed remotely for participants who have already been discharged from the hospital
- Concomitant medication (may be obtained/extracted from the medical record to minimize staff exposure to COVID-19)
- Study medication administration, if randomized to heparin and still hospitalized
- Local laboratory values, if applicable
- Assess need for inpatient medical services and complete ACTT

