5.2 Analysis Populations and Scopes

All analyses are based on 2 elements:

- Analysis population, which specifies which participants will be included in an analysis; and
- Data scope, which specifies the time window within which data will be included in an analysis

Five analysis populations are defined for this study.

The **Intent-to-Treat (ITT) population** will include all participants who are randomized. Participants will be analyzed according to the treatment group allocated by randomization.

The **modified Intent-to-Treat (mITT) population** will include all participants who are randomized and received at least one dose of study drug. Participants will be analyzed according to the treatment group allocated by randomization.

The **Per Protocol population** will include all participants who are randomized, receive all three doses of study drug post randomization or receive SoC drug through day 7, have no major deviations from the protocol that affect the primary endpoint, and complete all pre-specified study assessments/activities. Participants will be analyzed according to the treatment actually received.

The **Safety population** will include all participants who are randomized and receive at least one dose or part of a dose of study treatment post-randomization. Participants will be analyzed according to the treatment actually received.

The **All Screened population** will be defined as all participants with any data entered into the database.

The analysis populations will be listed by participant.

The ITT, mITT and Per Protocol data scope includes outcomes and events observed from a given participant’s date of randomization until either their final or Day 30 contact, determined by whichever occurs first. This will be applied mainly to the analyses of efficacy endpoints.

The ITT, mITT and Per Protocol data scope will also be used for the secondary safety endpoints of major or non-major clinically relevant bleeding through Day 30 and any bleeding through Day 30.

The on-treatment data scope will include all outcomes and events observed from randomization until 72 hours following permanent discontinuation of the study drug. This on-treatment data scope will be applied mainly to the analyses of safety endpoints.

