7.4 Significance

All statistical tests and confidence intervals will use a 2-sided analysis with a significance level of $\alpha = 0.05$.

8 Safety Analysis

The following safety analyses will be based on the Safety population and on-treatment data scope. Additional safety analyses are detailed in [Section 11.4](#).

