8.2.3 Other Adverse Events

Safety assessments will also include monitoring of serious adverse event(s) (SAE) and non-serious adverse event(s) (AE). Efficacy and safety endpoints that are adjudicated positively as study outcomes, including all bleeding events, will not be considered as AEs or SAEs.

All AEs will be collected from the time of randomization until the participant completes Day 30 or final contact, whichever is longer. All SAEs will be collected from the time of consent until the participant completes Day 30 or final contact, whichever is longer.

All reported AEs will be coded using the Medical Dictionary for Regulatory Activities (MedDRA).

Participant counts will be summarized using frequencies and percentages. A participant will be counted only once per category of summarization (e.g., if a participant has multiple AEs, the participant will only be counted once in the overall 'Any AE' row and will be counted once in each row for the specific AE category reported). Where participants have more than one level of severity/relatedness recorded only the highest level of severity/relatedness will be summarized.

Participant counts will be summarized by system, organ class and preferred term (PTm) by treatment group for treatment-emergent AEs (TEAEs) and by seriousness, relatedness.

An AE identified by the investigator as 'Related' or 'Potentially Related' or where relationship is missing will be considered 'related to study treatment.'

All AEs will be listed. Listings of SAEs, Related AEs, fatal and AEs of special interest (e.g., Overdose, misuse, or accidental exposure to study drug; medical error involving study drug), will also be listed. Additional details of SAEs and Deaths will also be listed.

Treatment Emergent is defined as any SAE/AE that has a start date during or after administration of the investigational product (i.e., randomized rNAPc2 or heparin treatment), post-randomization up to Day 30 or final contact.

Data will be displayed as collected in the clinical database. Adverse Events with missing start dates will be considered as treatment emergent.

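### SAP Section 8 and SAP 8.2.3 give different time windows for adverse events; if the Section 8 window governs, rNAPc2 is usually counted for less time than heparin

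*SAP*

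**What the plan says.** SAP 5.2 says that every analysis rests on a population and on a data scope, the scope being the time window for which data count. It then defines the safety window: "The on-treatment data scope will include all outcomes and events observed from randomization until 72 hours following permanent discontinuation of the study drug". It adds: "This on-treatment data scope will be applied mainly to the analyses of safety endpoints". One group of safety endpoints is taken out: the ITT, mITT and Per Protocol scope, which runs to the final or Day 30 contact, "will also be used for the secondary safety endpoints of major or non-major clinically relevant bleeding through Day 30", and likewise for any bleeding through Day 30. AEs and serious AEs (SAEs) are not named in that exception.

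The lead-in to SAP Section 8 reads: "The following safety analyses will be based on the Safety population and on-treatment data scope". Section 8.2.3 on adverse events comes under that lead-in. It collects AEs to Day 30 or final contact and defines treatment-emergent events as those starting during or after rNAPc2 or heparin treatment, "post-randomization up to Day 30 or final contact".

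Protocol 9.4.4 tabulates AEs from the whole study. Under Protocol 9.4.1 the SAP prevails where the two differ, and SAP Section 12 lists no change to the AE window.

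The two treatments differ in length. rNAPc2 is a fixed course on Days 1, 3 and 5. For heparin, the Day 8 and Day 30 visit descriptions in Protocol 8.1.3 both list: "Study medication administration, if randomized to heparin and still hospitalized".

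**The concern.** A window tied to the last dose is the same for both arms only if the arms are treated for the same time. Here one arm has a three-dose course and the other is treated for as long as the patient stays in hospital. Counting events to 72 hours after the last dose would therefore usually give heparin patients more days in which an event can be counted. The simple percentages planned in 8.2.3 would not correct for that.

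The cut-off also means different things for the two drugs. Protocol 6.5.1 says "half-life of rNAPc2 following the day 5 dose is approximately 72 hours", so 72 hours is about one half-life of rNAPc2 but 16 half-lives of low molecular weight heparin (72 / 4.5).

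The Phase 2b objective in SAP 2.1 includes an acceptable safety profile. If the window is left open, it can be settled after results are known, and one of the two choices favours rNAPc2 artificially.

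**Working it through.** The documents give no figure for this point, so there is nothing to reproduce.

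**Inputs.** Scope end: 72 h, or 3 days, after permanent discontinuation (SAP 5.2). rNAPc2 doses: Days 1, 3 and 5, with Days 3 and 5 each ±1 day (Protocol 6.5.1, 8.1.1). rNAPc2 half-life: 47.0–64.1 h after the first dose and 70.8–78.9 h after the third (Protocol 2.2). Low molecular weight heparin half-life: about 4.5 h (Protocol 6.5.1). Heparin continues while the patient is hospitalized (Protocol 8.1.3). The last dose is taken as permanent discontinuation, and heparin as study drug.

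**Step 1: scope end = last dose day + 3, capped at Day 30.** Days counted = scope end − 1.

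| Patient | Last dose | Scope end | Days counted | Ratio to full-course rNAPc2 |
|---|---|---|---|---|
| rNAPc2, full course | Day 5 | Day 8 | 7 | 1.00 |
| rNAPc2, two doses | Day 3 | Day 6 | 5 | 0.71 |
| rNAPc2, one dose | Day 1 | Day 4 | 3 | 0.43 |
| Heparin | Day 4 | Day 7 | 6 | 0.86 |
| Heparin | Day 5 | Day 8 | 7 | 1.00 |
| Heparin | Day 8 | Day 11 | 10 | 1.43 |
| Heparin | Day 15 | Day 18 | 17 | 2.43 |
| Heparin | Day 27 or later | Day 30 | 29 | 4.14 |

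With the ±1 day window, the full-course rNAPc2 scope ends between Day 7 and Day 9. Closing at Day 8 leaves out 22 of the 29 days to Day 30 (76%).

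**Step 2: fraction of drug left at 72 h = 2^(−72 / half-life)**, assuming single-exponential decline.
- After the third dose: 2^(−72/70.8) = 49.4% to 2^(−72/78.9) = 53.1%.
- After the first dose: 2^(−72/47.0) = 34.6% to 2^(−72/64.1) = 45.9%.
- Low molecular weight heparin: 2^(−72/4.5) = 2^(−16) = 0.0015%.

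**Step 3: illustration of the effect on AE incidence.** Assume the same constant hazard in both arms and a true risk R over 29 days. The risk counted over t days is 1 − (1 − R)^(t/29). Take t = 7 for rNAPc2, and t = 10 or 17 for heparin (last dose Day 8 or Day 15 for every patient).

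| Assumed R | rNAPc2, to Day 8 | Heparin, to Day 11 | Heparin, to Day 18 |
|---|---|---|---|
| 10% | 2.5% | 3.6% | 6.0% |
| 20% | 5.2% | 7.4% | 12.3% |
| 40% | 11.6% | 16.2% | 25.9% |
| 60% | 19.8% | 27.1% | 41.6% |

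Neither R nor the heparin duration is a Phase 2b figure from the documents. Day 15 borrows the Phase 3 planning assumption for median recovery on heparin (Protocol 9.2).

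**Step 4: bleeding through Day 8.** The primary safety endpoint (SAP 8.1) closes on Day 8, or two days after discharge when discharge comes before Day 8.
- Full course, last dose Day 5: the scope also ends on Day 8, so nothing is lost.
- One dose, discharged on Day 2: endpoint limit Day 4, scope end Day 4. Two doses, discharged on Day 4: both Day 6. Nothing is lost.
- One or two doses, still hospitalized: the endpoint runs to Day 8 but the scope ends on Day 4 or Day 6. Two to four days are lost.
- Any bleeding through Day 8 (SAP 8.2.2) has no discharge cap, so early-discharged patients can be cut short there too.

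**The case against.** The strongest reply is that the AE section already has an equal window. Section 8.2.3 collects and defines events to Day 30 in all arms, Protocol 9.4.4 agrees, SAP 5.2 says only that the scope applies mainly to safety endpoints, and SAP 4.2 lets a specific section override a general convention. This has force, and it is why the point is a contradiction and not a settled unequal comparison. It does not close the matter. Section 8.2.3 says which events are collected and which count as treatment-emergent, but assigns no data scope, and the 4.2 rule concerns display conventions.

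A reader might infer that the whole safety comparison, including bleeding, is biased toward rNAPc2. The documents do not support that. Day 30 bleeding is exempt, and the primary bleeding endpoint is untouched for a full course with the last dose on Day 5. Bleeds are not AEs or SAEs in this trial (Protocol 8.3, SAP 8.2.3), so the AE window does not alter the bleeding profile. Both rNAPc2 regimens share the same planned dosing days, so the planned scope is the same for both doses.

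Three further limits stand. Heparin patients whose last dose is on or before Day 5 have no longer window than a full-course rNAPc2 patient; the endpoints foresee discharge before Day 8, although exclusion criterion 6 removes patients expected to leave within 5 days. Permanent discontinuation is not defined for a completed course, and the Per Protocol definition sets study drug against SoC drug. If heparin is not study drug, its scope has no stated end, though 8.2.3 does count it as investigational product. Finally, Sections 8.1 to 8.2.3 plan counts and percentages without tests, and all AEs are listed, so no data are lost.

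**Conclusion.** The point holds as an unresolved conflict between the Section 8 lead-in and 8.2.3 over the AE and SAE window. It is conditional: AEs are compared over unequal periods only if the 72-hour scope governs. In that case the counted time is 7 days for a full rNAPc2 course against 10 days for a last heparin dose on Day 8 and 17 days for Day 15, and the distortion favours rNAPc2 with no true difference. For Day 8 bleeding the effect is confined mainly to rNAPc2 patients who stop early but stay in hospital, and to the any-bleeding table. The window lengths rest on treating heparin as study drug and the last dose as permanent discontinuation; the incidence figures also rest on an assumed constant hazard and an assumed heparin duration, and are illustrations only. The primary efficacy analysis is not affected. The conflict should be resolved before database lock because one reading biases the AE comparison.

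**What to change.** Amend the Section 8 lead-in in three respects.

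1. AE and SAE summaries use the Safety population with one fixed calendar window, from randomization to Day 30, identical in all arms and consistent with 8.2.3.
2. The 72-hour scope does not truncate the bleeding endpoints through Day 8 (8.1 and 8.2.2).
3. The 72-hour on-treatment scope is kept only as a labelled supplementary analysis, with permanent discontinuation defined for a completed rNAPc2 course and for heparin.

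The cost is SAP wording and one supplementary set of tables. AEs are already collected to Day 30, so no new data are needed. The small downside is that later events, less attributable to the drug, are counted in both arms.

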5.3 Subgroups

For the primary efficacy endpoint, the treatment effects across the following subgroup factors will be examined:

- D-dimer randomization stratification factor ($>$ vs. $\leq 2x$ local laboratory ULN)
- Treatment with an agent with demonstrated efficacy in patients with COVID-19, as described in [Section 6.2.1](#) (yes, no)
- Background antiplatelet therapy at baseline, as described in [Section 6.2.1](#)
- rNAPc2 dose regimen
- Initial heparin dosing strategy (prophylactic vs. therapeutic; within regimen comparison only)
- Severity of disease (as defined in [Section 14.1](#))
- Source of Laboratory Values used for primary endpoint determination (central vs. local)

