9.4 STATISTICAL ANALYSES

9.4.1 GENERAL APPROACH

The statistical analyses described in this section will be performed as further detailed in a separate statistical analysis plan. The statistical analysis plan will supersede the protocol in the event of any differences between the two documents in the plans for data analysis, and the protocol will be amended if appropriate. The statistical analysis plan will be included as an appendix in the clinical study report for this protocol.

Descriptive statistics for continuous variables will include the number of participants, mean and standard deviation, median, first and third quartiles, and minimum and maximum values. Descriptive statistics for categorical variables will contain count and percentage.

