9.4.7 SUBGROUP ANALYSES

For the primary efficacy endpoint for each Phase, the treatment effects across the following subgroup factors will be examined:

- D-dimer
- Gender
- Age group (<65, ≥65 years)
- Race/ethnicity
- Planned or ongoing therapy with an agent with demonstrated efficacy in patients with COVID-19 (yes, no)
- Baseline ACTT ordinal scale category
- Background antiplatelet therapy at baseline

For the Phase 2b primary efficacy endpoint, possible heterogeneity in the treatment effect for subgroups within each factor will be assessed by including the factor and the interaction between the factor and treatment in the analysis of covariance (ANCOVA) model.

Additionally, the heterogeneous application of heparin dichotomized by therapeutic vs. prophylactic uses, as well as the different standards of use across site, pose the need for sensitivity analyses to determine the degree to which the primary endpoint finding generalizes across sites.

Similarly, for the Phase 3 primary efficacy endpoint, possible heterogeneity in the treatment effect for subgroups within each factor will be assessed by including the factor and the interaction between the factor and treatment in the Cox proportional hazards model.

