7.2.3 Composite of Clinical Events

The secondary efficacy clinical composite will be measured and compared between treatment groups. This composite will consist of death (all-cause), thrombotic events (Stroke, MI, PE, peripheral arterial and clinically relevant deep vein thrombosis), organ support as defined in [Section 7.3.2](#), and rehospitalizations adjudicated as to its relatedness to COVID-19.

The primary formulation of the composite will limit the number of contributing events per component per patient to one, i.e., the aggregate will have values from 0 – 4 for each patient. The component-wise analysis will be performed using logistic regression, where the contribution of each component is necessarily a dichotomous variable. The aggregate will be analyzed using Poisson regression.

The secondary formulation will differ from the primary in that no limitation on the component-wise contributions will be imposed. Thus, component-wise analysis will also be Poisson regression except in the case of death or any data-driven circumstance where the only available values are binary.

Regression models will include treatment in the unadjusted formulation, and treatment, D-dimer stratum and pre-specified subgroups in the covariate-adjusted formulation. Pre-existing organ support of any modality is discussed below as an additional covariate, representing a special case arising from the specifications of the analysis.

Assumptions inherent to any of these models, e.g., whether data manifest in accordance with a Poisson distribution (where λ , the rate, is both mean and variance) will be tested. In the case of Poisson, testing significant deviations from assumptions will use Likelihood Ratio tests on Zero-inflated and/or Negative Binomial operationalizations of the dependent variable distribution (these are not mutually exclusive). Both Logistic and Poisson regression models may remove variables that introduce issues in the model estimation process, e.g., a regressor with no variance, cell sparsity, or sufficient multicollinearity to induce rank deficiency of the model-implied design matrix will flatten the likelihood function, destabilizing point estimates and inflating confidence intervals by orders of magnitude.

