11.1 Primary Efficacy Endpoint Sensitivity Analysis

As a sensitivity analysis, all types of missingness will be addressed via multiple imputation, with a target of 100 multiply imputed datasets. These analyses will be created for findings obtained initially with all available data, with subsequent analysis and pooling performed to evaluate if missing data produces bias in model point estimates or otherwise influences the inferential process.

Multiple imputation will be performed via PROC MI in SAS v9.4. The variables used in the imputation model are the six pre-specified sub-groups of interest, along with any relevant measurements for a subject that will better inform the imputation process (e.g., with missing Day 8 D-dimer, one would include baseline D-dimer in the model). The missing data mechanisms theoretically conferring unbiased estimation (given appropriate covariate selection in the imputation model) using this methodology are MCAR and MAR, although “modern” methodology (MI or FIML [full information maximum likelihood]) also demonstrates superior properties to listwise deletion et al in the MNAR case. Reference Appendices in [Section 14.2](#) which contain descriptions of the Bayesian models, methods for multiple imputation, and methods for power analysis used in this study.

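### SAP 5.3 omits the gender, age and race/ethnicity subgroups that Protocol 9.4.7 pre-specifies for the Phase 2b primary endpoint, with no record of the change, and the SAP body text does not name age in the models built from that list

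*SAP*

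**What the plan says.** Protocol 9.4.7 covers Phase 2b explicitly: "For the primary efficacy endpoint for each Phase, the treatment effects across the following subgroup factors will be examined". Its seven factors are D-dimer, gender, age group cut at 65 years, "Race/ethnicity", therapy with an agent of demonstrated efficacy in COVID-19, "Baseline ACTT ordinal scale category" and background antiplatelet therapy.

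SAP 5.3 opens almost identically, "For the primary efficacy endpoint, the treatment effects across the following subgroup factors will be examined", but its list is different: D-dimer stratum, COVID-19 agent, antiplatelet therapy, rNAPc2 regimen, initial heparin strategy, disease severity and laboratory source.

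Protocol 9.4.1 settles which list governs: "The statistical analysis plan will supersede the protocol in the event of any differences between the two documents".

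The SAP then reuses the list by reference. The adjusted composite models in 7.2.3 contain "treatment, D-dimer stratum and pre-specified subgroups in the covariate-adjusted formulation", with pre-existing organ support as one further covariate. For multiple imputation, 11.1 states: "The variables used in the imputation model are the six pre-specified sub-groups of interest". The same sentence goes on to admit other measurements that would inform the imputation. The Bayesian model in 11.2 uses the pre-specified subgroups, the D-dimer stratum and site. SAP 7.2.1 and 11.3 extend the subgroup and sensitivity analyses to the secondary efficacy endpoints.

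**The concern.** A reader of the protocol expects the D-dimer effect to be examined by age, gender and race/ethnicity. A statistician who follows the SAP would not produce those analyses, and nothing in the SAP says that the plan changed or why. If they were run later, they would no longer count as pre-specified.

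The trial enrols ages 18 to 90, and its Phase 2b data inform the Phase 3 dose regimen and possibly the eligibility criteria (SAP Section 1). Consistency of effect across these groups is therefore a natural question at the transition.

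The omission also carries into the models that borrow the list. Read literally, the adjusted 30-day composite, which includes death and organ support, adjusts for the laboratory that supplied the D-dimer value but not for age. Age, sex, race and ethnicity are all collected at screening (Protocol 8.1.3).

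**Working it through.** **1. The two lists side by side**

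| Protocol 9.4.7 | SAP 5.3 | Status |
|---|---|---|
| D-dimer | D-dimer stratum | kept |
| COVID-19 agent | COVID-19 agent | kept |
| Antiplatelet therapy | Antiplatelet therapy | kept |
| Baseline ACTT category | Disease severity (14.1) | replaced |
| Gender | none | dropped |
| Age group (<65, ≥65) | none | dropped |
| Race/ethnicity | none | dropped |
| none | rNAPc2 regimen | added |
| none | Initial heparin strategy | added |
| none | Laboratory source | added |

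Each list has seven factors. Three are kept, one is replaced, three are dropped and three are added.

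**2. Is the change recorded?** SAP Section 12 has four entries: the signed rank test, probability of discharge, the clinical composite, and adjudication of rehospitalizations. None concerns subgroups. The revision history for versions 2.0 and 3.0 is also silent on it.

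**3. Which list do the models use?** SAP 5.6 calls the rNAPc2 dose regimen a pre-specified subgroup of interest. That factor is on the SAP 5.3 list and not on the protocol's, so the phrase points to SAP 5.3.
- 7.2.3: age is not named. SAP 5.4 names only the D-dimer stratum as a covariate.
- 11.2: age is not named.
- 11.1: age is not named, but the open clause could admit it. The stated count of six does not match the seven factors in 5.3. Counting the D-dimer stratum separately, as 7.2.3 and 11.2 do, gives 7 − 1 = 6. Age is absent on either count.
- Appendix 14.2: only headings are legible in the text available, so its content is unknown and is not counted as a gap.

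Elsewhere, age, sex and race appear in the SAP as baseline descriptors (6.2), and age also in the age-calculation rule (4.2).

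**4. How informative would the age subgroups be?** The 160-participant row of the power table has 128 evaluable. Protocol 5.5 cites 46% of hospitalized patients as older than 65, used here as a proxy for ≥65. Then 0.46 × 128 ≈ 59 and 0.54 × 128 ≈ 69. With arms equal within each subgroup, the 95% half-width on the log scale is 1.96 × SD × √(4/n). The documents give no log SD; 0.63 is an assumption.
- n = 59: 1.96 × 0.63 × √(4/59) = 0.32
- n = 69: 1.96 × 0.63 × √(4/69) = 0.30
- Difference between subgroups: √(0.32² + 0.30²) = 0.44, a factor of exp(0.44) = 1.55

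All three scale with the SD. At an SD of 1.0 they become 0.51, 0.47 and 0.70.

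**5. How much could age matter in the composite?** The 1:1:2 allocation of 160 gives 80 pooled rNAPc2 against 80 heparin. The SD of the arm difference in the share of older patients is √(0.46 × 0.54 × 2/80) = 0.079. Suppose older patients carry RR times the event risk. An imbalance d then moves the unadjusted event ratio by (1 + (RR − 1)(0.46 + d/2)) / (1 + (RR − 1)(0.46 − d/2)).

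| Assumed RR | d = 1 SD | d = 2 SD |
|---|---|---|
| 2 | 1.055 | 1.114 |
| 3 | 1.086 | 1.179 |

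**The case against.** The protocol lets the SAP supersede it, and the revision history describes Section 12 as holding key changes, not every change. That makes the change permissible. It does not make it documented: no other place records it, and the protocol still promises the analyses.

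The protocol promises age only as a subgroup for the primary endpoint. It nowhere promises adjustment of the clinical composite for age, so that request is a recommendation and not a broken commitment. SAP 7.2.3 already adjusts for severity and pre-existing organ support, which may overlap with age. It also warns of cell sparsity and rank deficiency. This stands. It is the reason to add a single continuous covariate, and to keep gender and multi-level race/ethnicity from entering those models through an edit to 5.3.

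The subgroups would be weakly informative. A difference of 0.44 log corresponds to no reduction in one age group against about 35% in the other (1 − 1/1.55 = 0.35). This also stands, but the SAP keeps other subgroups at the same sample size, so low precision does not explain an unrecorded removal.

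Three stronger readings are tempting and are not supported:
- **Age is excluded from every model.** The open clause in 11.1 could admit it, and Appendix 14.2 could not be read.
- **The 6% to 18% shifts are bias.** They are chance imbalance under randomization, which the sampling error of the unadjusted analysis already covers. They also rest on an assumed risk ratio and ignore overlap with the other covariates.
- **The trial could say nothing about older patients, women or race groups.** The data are collected and summarized by arm, so the question stays open to unplanned exploratory analysis. What is lost is pre-specification.

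**Conclusion.** The point holds as a documentation and completeness defect with modest analytic consequences. Three of the protocol's seven pre-specified subgroup factors disappear from the governing document without substitute, record or reason. That conclusion rests on the text alone. The primary rank sum test uses no covariates and is unaffected.

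The SAP body does not name age in 7.2.3 or 11.2 and leaves it to discretion in 11.1. Naming it would improve precision in the adjusted composite and correct chance imbalance; it would not remove bias. A one-SD imbalance of 7.9 points would move the unadjusted event ratio by about 6% to 9%, and a two-SD imbalance by about 11% to 18%, if older patients have two to three times the risk. That risk ratio, the 46% share and the log SD of 0.63 are planning assumptions and not trial data.

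**What to change.** - Restore gender, age group (<65, ≥65) and race/ethnicity to SAP 5.3 as exploratory subgroups of the primary endpoint, run in 11.2 one factor at a time. Alternatively, record and justify their removal in Section 12.
- State that gender and race/ethnicity are not thereby added to the 7.2.3 regressions. Because 7.2.3 and 11.1 cite the list by reference, an edit to 5.3 alone would carry them in.
- Add age as one continuous covariate to the 7.2.3 adjusted models, and name it in the 11.1 imputation model.
- Reconcile the six subgroups of 11.1 with the seven of 5.3, preferably by listing the imputation variables by name.

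The cost is SAP wording and a few more model runs on data already collected. The downside is three imprecise exploratory factors, with the widths shown above for age, and one more covariate in models where the SAP already anticipates sparse cells.
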